- Amount of total daily insulin doses (units) utilized per day during therapy among patients with type 2 diabetes, compared between treatment arms and to a prior to enrollment outpatient insulin regimen
- serum potassium covariate adjusted for baseline with attention to both elevation and depression

Single-Center Exploratory Outcomes at Vanderbilt University Medical Center

The following exploratory outcomes will only be performed in patients at Vanderbilt University Medical Center who elect to participate in a sub-study. Patients can decline to participate in this sub-study and still participate in parent clinical trial. To explore changes in the plasma proteome during IV diuresis, we will collect one 15mL blood sample (10mL in purple top EDTA tube and 5mL in red top tube) at baseline and on the final study day (Day 5 or discharge).

2.4 Safety Outcomes: Compared between treatment arms during the index stay from signing of informed consent to hospital discharge

- Change in the estimated Glomerular Filtration Rate by the MDRD equation at discharge adjusted for baseline
- Incidence of ketoacidosis, identified by the study team as elevated ketones in the urine and an arterial blood pH < 7.35 and adjudicated by the Clincal Events Committee
- Serum glucose covariate adjusted for baseline with attention to both elevation (> 400mg/dl) and depression (< 70mg/dl)
- Potential prolonged hospitalization as a result of hypoglycemia requiring medical intervention as adjudicated by the Clinical Events Committee
- Potential prolongation of hospitalization as a result of incidence of hypovolemic hypotension, defined as a symptomatic hypotension with a sustained systolic blood pressure less than 90 mmHg over 30 minutes and requiring medical intervention as adjudicated by the Clinical Events Committee. All hypotension episodes requiring medical intervention will be evaluated by the Clinical Events Committee.
- Inpatient mortality

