7.4 Reporting of Adverse Events and SAEs

All adverse events occurring from signing of the Informed Consent through the 30-day follow-up period will be collected and reported. The Site Investigator is responsible for monitoring the safety of patients enrolled into the study. The following adverse events are anticipated, disease related-events in patients with decompensated heart failure; however, they should still be reported on the Adverse Event form in the REDCAP Database (some may require reporting as study endpoints):

- New Ventricular Arrhythmia: Ventricular tachycardia lasting longer than 30 seconds, or frequent non-sustained VT causing hemodynamic instability with MAP < 60 mmHg requiring intervention or > 1 intra-cardiac defibrillation or external cardiac defibrillation shock or ventricular fibrillation requiring defibrillation or requiring transfer to the intensive care unit
- Hypotension: SBP < 90 for 2 repeated measurements within 30 minutes or lasting at least 30 minutes or symptomatic hypotension necessitating clinical intervention (defined as vasopressor support, intravenous fluid boluses, or initiation of inotropes)
 - Hypovolemic hypotension: subset of "hypotension" requiring fluid administration for hypovolemia
- *Cardiac arrest*: any ventricular arrhythmic or pulseless electrical event that requires immediate life-sustaining medical therapies
- Acute kidney injury requiring renal replacement therapy: an acute renal failure event that began during the study period and necessitates new renal replacement therapy during the hospitalization
- Prolonged hospitalization as a result of the following safety outcomes: hypotension requiring medical intervention or hypoglycemia requiring medical intervention
- Diabetic ketoacidosis as adjudicated by the CEC
- Death

All serious adverse events must be recorded in the Adverse Event Record of the patient's REDCAP database. All serious adverse events should be monitored until stabilization or resolution.

The process of reporting of SAEs will be as follows:

- 1. The investigator team informs the site investigator of an SAE
- 2. The site investigator reports the SAE to the local IRB and to the coordinating center and PI within 24 hours of being aware of the event. The site investigator will electronically submit the necessary supporting documentation to the coordinating site.
- 3. The coordinating center and PI will report the SAE to AstraZeneca.

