 - a. Repeated as per doubling of the cumulative Day 2 loop diuretic dose (log2 cumulative loop diuretic dose centered at 40mg)
- d) Spot urine sodium-based diuretic efficiency defined as the spot urine sodium concentration (mmol/L) on Day 2 per 40mg of IV furosemide equivalents (preceding loop diuretic dose)
- e) Fractional excretion of sodium (FENa)-based diuretic efficiency on Day 2 of IV therapy defined as the FENa from a spot urine test on Day 2 of IV therapy collected ~2 hours after bolus loop dose per 40 mg of IV furosemide equivalents.
 - a. Repeat as per doubling of the cumulative loop diuretic dose (log2 cumulative loop diuretic dose centered at 40mg)
- f) Urinary Na/K ratio at Day 2 of IV therapy adjusted for baseline.
- g) Calculated 6-hour sodium output on Day 2 of IV therapy using spot urine sodium collected 2 hours after bolus loop dose.
- h) Length of hospital stay, measured as days from admission to discharge
- i) Presence of symptoms of congestion and dyspnea at discharge, measured via blinded-physician exam and patient reported congestion scores.
- j) Hospital readmission within 30 days of discharge for any cause.
- k) Number of days at home without hospitalization or emergency room visit during 30-day follow up period.
- 1) Mean serum glucose during therapy
- m) Amount of total daily insulin doses (units) utilized per day during therapy, compared between treatment arms and to a "prior to enrollment" outpatient insulin regimen.
- n) Analyze the change in basic metabolic panel laboratory values and hemoglobin from baseline to end of study
- o) Serum potassium covariate with attention to both elevation and depression.

Hypokalemia levels are defined as

- a. Not hypokalemic: serum potassium > 3.4 mEq/L
- b. Mild: serum potassium 3.0 3.4 mEq/L
- c. Mod-Severe: serum potassium < 3.0 mEq/L

Hyperkalemia levels are defined as

- a. Not hyperkalemic: serum potassium < 5.1 mEq/L
- b. Mild: serum potassium 5.1 5.5 mEq/L
- c. Severe: serum potassium > 5.5 mEq/L

Safety Endpoints: Comparing differences among the two arms in the following:

- a) Estimated Glomerular Filtration Rate by the MDRD equation at discharge adjusted for baseline. A sensitivity analysis of eGFR by the CKD-EPI equation will also be done.
- b) Incidence of ketoacidosis as adjudicated by the CEC
- c) Serum glucose with attention to both elevation and depression.
 - a. Hypoglycemia is defined as:
 - i. Not hypoglycemic: serum glucose > 70 mg/dl

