Inpatient and 30-day endpoints of interest will be summarized overall and by treatment assignment. Categorical variables will be described using frequencies and proportions; continuous variables will be described using means and standard deviations as well as medians and interquartile ranges (IQR). Missingness will be recorded for each variable. For those endpoints that are a composite of multiple endpoints, such as incidence of worsening heart failure (requiring IV inotropic therapy, new admission to an ICU, new non-invasive positive pressure ventilation with bi-level positive airway pressure, or increase in the IV diuretic protocol intensity by 2 rows after Day 1 as adjudicated by the CEC) and hospital readmission within 30 days of index hospitalization discharge (for heart failure-related reasons or diabetic reasons), frequencies will be summarized overall and for each level.

No statistical testing will be done to compare characteristics across groups.

Main Analysis

All model results (unadjusted and adjusted) will be summarized with point estimates, 95% confidence intervals (CIs), and p-values displayed in tabular form or graphically, along with appropriate model fit statistics. Missingness in adjusting covariates will be addressed using multiple imputation based on predictive mean matching.

Primary Analysis: Our main analysis will be a covariate-adjusted proportional odds (PO) regression model with our outcome being cumulative change in weight per 40mg of IV furosemide equivalents from

enrollment to the minimum of Day 5 or discharge and the main predictor being treatment assignment. Adjusting covariates will be pre-specified and include baseline weight. Baseline weight will be fit with restricted cubic splines with 3 knots to relax the linearity assumptions.

Secondary Analyses:

Appropriate model diagnostics will be run to assess model fit. If model diagnostics suggest the planned approach violates necessary assumptions, alternative methods will be pursued.

- a) Binary logistic regression will be used to assess the association of the incidence of worsening heart failure as adjudicated by the CEC with treatment assignment.

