- h) The association of length of hospital stay with treatment assignment will be analyzed using the Wilcoxon Rank Sum test

- The association of presence of symptoms of congestion and dyspnea at discharge measured via blinded physician exam and patient reported congestion scores with treatment assignment will be analyzed using the Pearson chi-square test. A proportional odds model will be used to assess the association of discharge congestion score with treatment assignment, adjusting for baseline congestion.
- j) Cumulative incidence of all cause hospital readmission within 30 days of index hospitalization discharge will be graphed by treatment arm treating death as a competing risk. The association of all cause hospital readmission within 30 days of index hospitalization discharge with treatment assignment will be analyzed using the Pearson chi-square test.
- k) The association of number of days at home without hospitalization or emergency room visit during the 30-day follow-up period with treatment assignment will be analyzed using the Wilcoxon Rank Sum test. For purposes of analysis, subjects who died within 30 days of the index hospital discharge will be assigned a value of 0 days at home
- 1) The association of mean serum glucose during therapy with treatment assignment will be analyzed using the Wilcoxon Rank Sum test
- m) Total daily insulin doses (units) utilized per day during therapy will be compared between treatment arms in all comers and in those with diabetes at baseline using a Wilcoxon Rank Sum Test. Total daily insulin doses utilized per day during therapy will be compared to a 'prior to enrollment' utilization using the Wilcoxon Signed Rank Test.
- n) The change in basic metabolic panel laboratory values and hemoglobin from baseline to the end of study will be compared across treatment groups using the Wilcoxon Rank Sum test.
- o) Serum potassium trends over time by treatment assignment will be graphed. Descriptive statistics
 of the daily raw potassium values and kalemic status during hospitalization by treatment group
 will be reported and compared across treatment assignments by Wilcoxon Rank Sum tests and
 Pearson's chi-square tests, respectively.

Safety Analyses:

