All multivariable models will adjust for the same key covariates as specified for the primary outcome, as sample size permits. Appropriate model diagnostics will be run to assess model fit. If model diagnostics suggest the planned approach violates necessary assumptions, alternative methods will be pursued.

- a) The association of estimated Glomerular Filtration Rate (eGFR) at discharge, calculated using the MDRD equation, with treatment assignment will be modeled using covariate-adjusted PO regression, adjusting for baseline eGFR. The analysis will be repeated calculating eGFR using the CKD-EPI equation as well.
- b) The association of the incidence of ketoacidosis as adjudicated by the CEC with treatment assignment will be analyzed using the Pearson chi-square test.
- c) Serum glucose trends over time by treatment assignment will be graphed. Descriptive statistics of the daily raw glucose values and the glycemic status during hospitalization by treatment group will be reported and compared across treatment assignment by Wilcoxon Rank Sum tests and Pearson's chi-square tests, respectively.
- d) The association of incidence of hypovolemic hypotension, defined previously, with treatment assignment will be analyzed using the Pearson chi-square test.

e) The association of inpatient mortality with treatment assignment will be analyzed using the Pearson chi-square test and univariate logistic regression.

Sensitivity Analyses:

Our sensitivity analysis will be a covariate-adjusted proportional odds (PO) regression model with our outcome being log-transformed weight at the minimum of Day 5 or discharge and the main predictor being treatment assignment. Adjusting covariates will be as defined in the primary analysis. Appropriate model diagnostics will be run to assess model fit. If model diagnostics suggest the planned approach violates necessary assumptions, alternative methods will be pursued.

Heterogenicity of Treatment Effect:

Heterogenicity of Treatment Effect (HTE) will be assessed refitting the primary model with the covariate of interest interacted with treatment assignment. The HTE analysis will include the following variables:

- Sex (male or female)
- Baseline edema score (No-Mild/Moderate/Severe)
- Baseline NTproBNP
 - Continuous
 - Dichotomize by median NTproBNP [above/below]
- Baseline BMI-adjusted BNP: defined as a 4% increase in NT-proBNP for every 1 unit increase in baseline BMI above a BMI of 20kg/m²
 - Continuous

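### The discharge eGFR analysis has no place for new renal replacement therapy, and no analysis compares that event between arms; a worst rank and a by-arm count would close the gap cheaply

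*SAP*

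**What the plan says.** The SAP's first safety endpoint is "Estimated Glomerular Filtration Rate by the MDRD equation at discharge adjusted for baseline", with CKD-EPI as a sensitivity analysis. Under Safety Analyses a), eGFR "at discharge, calculated using the MDRD equation, with treatment assignment will be modeled using covariate-adjusted PO regression, adjusting for baseline eGFR". Neither place says what value a patient on new renal replacement therapy receives, or how a patient without a discharge value enters.

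The only imputation rule, under Main Analysis, is "Missingness in adjusting covariates will be addressed using multiple imputation based on predictive mean matching". It covers covariates, not outcomes.

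Protocol section 7.4 lists acute kidney injury requiring renal replacement therapy among the anticipated events to be recorded, and defines it as "an acute renal failure event that began during the study period and necessitates new renal replacement therapy during the hospitalization". The SAP names this event in no endpoint, analysis or table. It is also absent from the list of events for the Clinical Event Committee in Protocol 5.4.

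The timing of the last sample is not settled. Protocol 2.4 describes the safety outcomes as "Compared between treatment arms during the index stay from signing of informed consent to hospital discharge", and the SAP speaks of discharge. The schedule in Appendix A takes the last serum chemistry on Day 5, or at discharge if that is earlier.

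Protocol 2.1 says that the trial is also meant to establish safety, and names renal outcomes among the areas covered.

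**The concern.** Both equations turn a measured serum creatinine into a filtration estimate. While a patient is being dialysed, that creatinine partly reflects the treatment, so the computed eGFR can overstate native kidney function. The planned model ranks the patient by that number, and one of the worst kidney outcomes can land among the ordinary values. A patient who dies without a final value has no outcome, and no rule supplies one, so a standard fit leaves that patient out.

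Both effects favour the arm with more such patients. The trial aims to say something about kidney safety even if the primary endpoint is not met, so its main kidney analysis should be able to register these events. Exploratory analysis n), which compares changes in the metabolic panel by Wilcoxon test, has the same gap for creatinine.

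**Working it through.** **Inputs.** The SAP (Power and Sample Size) gives 120 patients per arm. The documents give no power, margin or event rate for eGFR. The stated 87% power concerns the primary endpoint and plays no part here. All event counts below are assumptions.

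**Scale.** Let P be the probability that a random control patient has a better value than a random dapagliflozin patient, so 0.5 means no difference. The calculation is unadjusted, as an approximation to the proportional odds (PO) fit adjusted for baseline eGFR.

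Standard error under no difference = sqrt((n1 + n2 + 1) / (12 × n1 × n2)) = sqrt(241 / (12 × 120 × 120)) = sqrt(241 / 172,800) = 0.0373.

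**Two misranked patients in one arm.** A patient ranked last wins none of the comparisons with the other arm. A patient ranked mid-range wins half of them, and one ranked at the top wins all.
- Mid-range instead of last: 2/120 × 0.5 = 0.0083, and 0.0083 / 0.0373 = 0.22 standard errors.
- Top instead of last: 2/120 × 1 = 0.0167, and 0.0167 / 0.0373 = 0.45 standard errors.

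**Larger imbalances.** Assume that half of the affected patients are dialysed, with a final value averaging 0.5 SD below the mean. The other half die without a value, and everyone else is alike in both arms. If a share q1 (dapagliflozin) and q0 (control) of the analysed patients is ranked last, then P = 0.5 + (q1 − q0)/2.

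| Dialysis or death, dapagliflozin vs control | As planned (simulated) | Dialysis last, deaths left out | Dialysis and deaths last |
|---|---|---|---|
| 6 vs 2 | 0.502 | 0.5 + (3/117 − 1/119)/2 = 0.509 | 0.5 + (6/120 − 2/120)/2 = 0.517 |
| 10 vs 2 | 0.505 | 0.5 + (5/115 − 1/119)/2 = 0.518 | 0.5 + (10/120 − 2/120)/2 = 0.533 |
| 12 vs 2 | 0.506 | 0.5 + (6/114 − 1/119)/2 = 0.522 | 0.5 + (12/120 − 2/120)/2 = 0.542 |

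Simulation of the last column gave 0.516, 0.534 and 0.542, in agreement with the formula.

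The simulated chance of p < 0.05, as planned and with dialysis and deaths both ranked last, was:
- 3 vs 1: 5.0% and 5.3%
- 6 vs 2: 5.0% and 5.9%
- 10 vs 2: 5.5% and 13.6%
- 12 vs 2: 5.2% and 17.2%

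The planned analysis stays close to 0.50 whatever the imbalance. Worst ranking moves P the right way, but the power gained is modest. A direct Fisher test of the 12 vs 2 counts of dialysis or death gives p = 0.011, so the by-arm count is the more sensitive display.

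**The case against.** The strongest reply is that these events are not lost to the trial. In Safety e), "The association of inpatient mortality with treatment assignment will be analyzed using the" Pearson chi-square test and a logistic regression. New renal replacement therapy is recorded as an adverse event, and adverse event reports go to the DSMB at each meeting. All of this stands. A reader might infer that the worst renal outcomes disappear from the trial, or that Safety a) is the only kidney analysis. The documents support neither: the gap lies in this model and in exploratory n), and in the lack of any by-arm comparison of new renal replacement therapy.

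A second reply is that the distortion of creatinine is inferred. The plan does not say which creatinine a dialysed patient contributes, and one who has come off dialysis with recovered function is ranked fairly by the measured value. This also stands. It limits the misranking to patients still on dialysis at the final sample. Chemistries are taken daily, so a patient who dies has earlier values, but the SAP gives no rule for using them.

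A reader might also infer that the rule hides harm from dapagliflozin. That holds only if the events fall mainly in that arm. If they fall in the control arm, the same rule hides a benefit.

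A third reply is that all-cause death does not belong at the bottom of a kidney scale and is already compared elsewhere. This is a fair dispute. The SAP does accept the principle for days at home, where "subjects who died within 30 days of the index hospital discharge will be assigned a value of 0 days at home", but that is not a kidney measure. Death therefore belongs in a sensitivity fit and not in the main definition.

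**Conclusion.** The point holds as a cheap improvement to the safety analysis. Followed as written, Safety a) ranks a patient still on dialysis by a creatinine that dialysis may have lowered and leaves out a patient who dies without a final value. New renal replacement therapy is compared between arms nowhere.

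The numerical effect is negligible with one to three events per arm. On the assumptions above it becomes noticeable only with a clear imbalance, of about 10 or more against 2. The documents give no rates, so they cannot show which case applies. The bias favours whichever arm has more such events. No primary or secondary conclusion depends on it.

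**What to change.** In SAP Safety a):

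1. Rank patients with new renal replacement therapy before the final sample below every measured eGFR. Fit the same PO model adjusted for baseline eGFR, for both MDRD and CKD-EPI.
2. State whether the final sample is Day 5 or discharge for patients who stay longer than five days. If it is Day 5, later dialysis or death is not reflected, and the text should say so.
3. Beside the model, report by arm the number with new renal replacement therapy and the number who died without a final value.
4. Keep the eGFR-only fit as a supplement.
5. Add a sensitivity fit that ranks death without a final value as worst.

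Exploratory n) should carry a note that its creatinine comparison has the same limit.

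The cost is a few lines of SAP text. The data are already collected and the model does not change. The downside is that the outcome is no longer a pure laboratory value, and a patient who recovered after dialysis is placed last. The eGFR-only fit shows that patient's measured value.

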Congestion remains the major cause of hospital readmission for heart failure and an inpatient plan of care that allowed more effective decongestion would be rapidly and widely adopted by the medical community. Therefore, we propose to test the

decongesting effects of the SGLT2 inhibitor dapagliflozin in patients with or without Type II diabetes admitted with an acute decompensation of chronic heart failure.

2.0 Study Outcomes:

- 2.1 Primary Outcome
- The change in weight in kilograms per 40mg of IV furosemide equivalents from enrollment baseline to day 5 or discharge (if earlier)
 - Standing weights will be performed by study personnel using the same scale throughout the study period with the same clothing (hospital gown without shoes). The patient will be requested to empty their bladder and bowels if needed prior to each weight assessment.
 - The cumulative loop diuretic dose includes all IV and oral doses administered in the study period, converted to IV furosemide equivalents. Diuretic conversion: 80mg oral furosemide = 40mg IV furosemide = 20mg oral torsemide = 1mg oral/IV bumetanide

This primary outcome investigates the decongestive potential of dapagliflozin by its impact on diuretic efficiency. Higher diuretic efficiency has been associated with better outcomes in multiple AHF populations.^{13,14} The primary outcome does not quantify the importance of initiating a mortality reducing therapy during hospitalization, which increases chronic adherence. Therefore, even if dapagliflozin does not meet the primary endpoint, this study would still be beneficial to establish the safety and best practices of initiating dapagliflozin during an AHF hospitalization, setting the stage for continuing it into the outpatient setting. The established benefits of such a strategy would emerge over the coming months to years. In addition to mechanistic and diuretic endpoints, additional secondary outcomes are designed to establish the safety across hemodynamic, renal, and glycemic outcomes.

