10.0 Statistical Methods

The full statistical methods are detailed separately in the Statistical Analysis Plan.

The primary analysis model will be the semiparametric proportional odds (PO) ordinal logistic regression model¹⁶ for continuous outcome variables¹⁷. The PO model does not make any distributional assumption for the response variable, is robust to extreme values, and is invariant to transformations of the response variable. It is also extremely efficient when compared to linear regression if normality holds. The Wilcoxon nonparametric two-sample test is a special case of the PO model, but the PO model allows for baseline covariate adjustment. Note that we use covariate adjustment instead of change from baseline so as to not assume that (1) the baseline variable is linearly related to the response variable and (2) the slope of the baseline variable is 1.0.

For binary outcomes we will use the special case of the PO model that is the binary logistic regression model.

For safety analysis of clinical lab variables we use the most powerful and least arbitrary continuous variable analyses and include the empirical cumulative distribution function of post-randomization values of these variables. These continuous analyses will also provide estimates of incidence of such outcomes as hyper- and hypo-kalemia, but will be more sensitive than using only binary responses.

Trial	Experimental agent	Mean decrease in weight (kg) Experimental, (%)	Mean decrease in weight Control, (%)	Within group SD in Experimental Group (kg)
TRUE-AHF ⁸	Ularitide			
RELAX-AHF ¹⁸	Serelaxin	3.6	3.0	4.4
ASCEND-HF ⁹	Nesirtide			
EVEREST ¹⁹	Tolvaptan	3.3	2.7	3.3
TACTICS ²⁰	Tolvaptan	3.7	2.5	4.4
Secrets of HF ²¹	Tolvaptan	3.5	2.4	2.0
ROSE-HF ²²	Nesiritide	3.25	3.5	0.9
ROSE-HF ²²	Dopamine	3.4	3.5	0.9
MEAN		3.5	2.9	2.7

Changes in body weight from admission to discharge in previous literature

Changes in weight by IV 40mg Furosemide Equivalents (FE)

Trial	Experimental agent	Duration (days)	Daily IV loop diuretic dose in FE, mean or median (IQR)*	Median (IQR) decrease in weight (kg)/40mg IV FE	Difference associated with adverse HF outcomes
RELAX-AHF ²³	Serelaxin	5	80	0.42 (1.00, 0.14)	Below median value
DIUR-HF ¹⁴	None	3-5	137 (100, 200)	0.20 (0.281, 0.082)	Below median value
ASCEND-HF ²⁴	Nesiritide	2		0.42 (1.0, 0.05)	Below median value
PROTECT ²⁵	Rolofylline	4	80 (47, 133)	0.38 (0.8, 0.13)	Below median value
EVEREST ^{19,26}	Tolvaptan	4	80	0.30 (0.79, 0.03)	Below median value

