 - ii. Mild: serum glucose 54-69 mg/dl
 - iii. Mod-Severe: serum glucose < 54 mg/dl
 - b. Hyperglycemia is defined as:
 - a. Not hyperglycemic: serum glucose < 200 mg/dl
 - b. Mild: serum glucose 200-300 mg/dl
 - c. Severe: serum glucose > 300 mg/dl
- d) Incidence of hypovolemic hypotension, defined as symptomatic hypotension with a sustained systolic blood pressure less than 90 mmHg lasting at least 30 minutes requiring fluid administration.
- e) Inpatient mortality

Design Considerations

Randomization

Patients will be randomized in a 1:1 ratio to receive either intervention or structured usual care. Randomization will use block randomization stratified by site with block sizes of 4.

Power and Sample Size

We anticipate dapagliflozin will increase the weight loss while decreasing the cumulative furosemide dose required to achieve euvolemia. On the basis of the historical literature, we project an increase in diuretic efficiency by 0.1kg/40mg IV furosemide in the Dapagliflozin arm to be a clinically meaningful difference. We project that our diuretic protocol will decrease variations in loop diuretic dosing, which drive large standard deviations. We project a normally distributed standard deviation within each arm to be 0.25kg/40mg. A sample size of 120 experimental subjects and 120 control subjects will have 87% power to detect a probability of 0.611 that an observation in the Dapagliflozin arm is less than an observation in the structured usual care arm using a Wilcoxon (Mann-Whitney) rank-sum test with a 0.05 two-sided significance level.

Statistical Approach

Descriptive Analysis

Initially, we will describe the study cohort pooled across all sites, both overall and grouped by treatment assignment. To characterize the study sample, demographic, clinical, and lab data will be described overall and by treatment arm. Categorical variables will be described using frequencies and proportions; continuous variables will be described using means and standard deviations as well as medians and interquartile ranges (IQR). Missingness will be recorded for each variable. To further assess the distribution of variables, graphical summaries will be displayed using graphs such as box-plots, dot-plots,

violin-plots, and/or histograms. No statistical testing will be done to compare characteristics across groups. At a minimum, the following baseline variables will be described:

- Age (years)
- Sex

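### Ketoacidosis and hypovolemic hypotension have a chi-square test but no between-arm estimate or interval, and the odds ratio planned for death is not finite if an arm has no deaths

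*SAP*

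**What the plan says.** SAP, Safety Analyses, treats the three clinical events as follows.

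- Item b): "The association of the incidence of ketoacidosis as adjudicated by the CEC with treatment assignment will be analyzed using the Pearson chi-square test".
- Item d), hypovolemic hypotension: the same test, and nothing further.
- Item e): "The association of inpatient mortality with treatment assignment will be analyzed using the Pearson chi-square test and univariate logistic regression".

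SAP, Main Analysis, promises point estimates, 95% confidence intervals and p-values for all model results. SAP, Description of Endpoints, provides for counts and proportions by arm. The Safety Analyses open with a general clause allowing other methods if diagnostics show that assumptions fail, without naming any.

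Protocol 10.0 leaves the full methods to the SAP but states: "For binary outcomes we will use the special case of the PO model that is the binary logistic regression model". Protocol 2.1 says that, even if the primary endpoint is missed, "this study would still be beneficial to establish the safety and best practices of initiating dapagliflozin during an AHF hospitalization".

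**The concern.** A chi-square test is not a model, so the SAP's promise of estimates and intervals does not reach items b) and d). What is pre-specified for those events is a count per arm and a p-value. If events are few, that p-value will usually exceed 0.05 whether or not dapagliflozin adds risk, and it does not say how large an excess remains possible.

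For death, an odds ratio with an interval is planned, but ordinary maximum likelihood fails when an arm is empty, which is most likely when deaths are few. The replacement would then be chosen after the data are seen, in an open-label trial.

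At stake is the secondary justification for the trial in Protocol 2.1. A statement about safety needs a bound on excess harm, and for two of the three events none is planned.

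**Working it through.** **Inputs.** 120 patients per arm (SAP, Power and Sample Size), assuming all are analysed. Two-sided 0.05 is stated for the primary endpoint only; I apply it to the safety tests. Neither document gives an event rate for any of the three events, so the rates below are assumptions, shown as a range.

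**The plan's own figure.** The only power figure concerns the primary endpoint: "A sample size of 120 experimental subjects and 120 control subjects will have 87% power to detect a probability of 0.611", from a difference of 0.1 and an SD of 0.25 kg per 40 mg. P = Φ(0.1/(0.25·√2)) = 0.611, as stated. The normal-means formula gives Φ(0.1/(0.25·√(2/120)) − 1.96) = Φ(3.098 − 1.96) = 87%; simulated Wilcoxon power is 85.3%. The figure reproduces to within 2 points and has no bearing on the safety events.

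**What the chi-square can return.** With a and b events, pooled p = (a+b)/240 and X² = ((a−b)/120)² / [p(1−p)·2/120].

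- 0 vs 0: p = 0, so the statistic is undefined.
- 3 vs 0: 0.025² / (0.0125·0.9875·2/120) = 3.04, p = 0.081.
- 4 vs 0: X² = 4.07, p = 0.044. With an empty control arm, significance therefore needs at least 4 events.

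**Power.** If the control risk is 0%, power is P(Bin(120, π) ≥ 4): 22% at π = 2% and 86% at π = 5%. Exact enumeration over two binomials gives the rest.

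| Risk, dapagliflozin vs control | Chi-square power |
|---|---|
| 2% vs 0% | 22% |
| 2% vs 1% | 7% |
| 3% vs 1% | 17% |
| 4% vs 2% | 13% |
| 5% vs 0% | 86% |
| 10% vs 2% | 79% |

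The test's actual type I error is 2.0% at 1% risk in both arms and 4.4% at 2%, so it is not inflated.

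**Empty arms.** With equal risk π and q = (1−π)^120, P(at least one arm empty) = 2q − q², and P(exactly one) = 2q − 2q².

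| π | q | At least one empty | Exactly one empty |
|---|---|---|---|
| 0.5% | 0.548 | 80% | 50% |
| 1% | 0.299 | 51% | 42% |
| 2% | 0.089 | 17% | 16% |
| 3% | 0.026 | 5% | 5% |

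In a 3 vs 0 table the fitted log odds ratio runs 7.9, 17.9, 27.9 after 10, 20 and 30 iterations, and its standard error reaches 396,046. A profile-likelihood interval still gives a lower limit for the odds ratio, 1.13. That limit excludes 1 while Pearson gives p = 0.081 on the same table, so an unnamed fallback could change the reading.

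**What an interval would show.** For 0 vs 0, the Miettinen-Nurminen limit d solves d² = 3.84·(240/239)·d(1−d)/120, so d/(1−d) = 0.0321 and d = 3.1 points.

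| Events | Pearson p | Miettinen-Nurminen 95% CI for risk difference (points) |
|---|---|---|
| 0 vs 0 | undefined | −3.1 to +3.1 |
| 2 vs 1 | 0.56 | −3.1 to +5.1 |
| 3 vs 0 | 0.081 | −0.6 to +7.1 |

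Newcombe limits are close: −3.1 to +3.1 for 0 vs 0 and −1.0 to +7.1 for 3 vs 0.

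**The case against.** The strongest reply is that this is a reporting gap. Counts by arm are planned, so anyone can compute the intervals, and the binding limit is 120 per arm: the better analysis still leaves about 3 points open at 0 vs 0. That stands, and it rules out a conclusion a reader might draw, that the choice of test is what prevents a safety conclusion. It does not make a pre-specified interval unnecessary, because a p-value hides that limit.

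A reader might also infer that none of the three events has an interval. That is true only on the risk-difference scale; for death the SAP promises an odds ratio with a 95% CI. Separation would be noticed at fitting, the fallback clause would apply, and a profile-likelihood bound survives. These points stand, but the clause names no method and does not clearly reach items b) and d), which have no model.

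Rarity is an assumption. It is least secure for hypovolemic hypotension, since both arms have loop diuretics titrated to a urine-output goal. At higher rates the test has reasonable power.

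Finally, the safety case is broader than these events: it includes eGFR by proportional odds regression, glucose, adjudication and a safety board. That is true, but none of these bounds the excess risk of ketoacidosis, hypotension or death.

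**Conclusion.** The concern holds in limited form. Ketoacidosis and hypovolemic hypotension have no pre-specified between-arm estimate or interval, and this does not match Protocol 10.0. Death has a planned odds ratio whose ordinary estimate and Wald interval can fail, with no named replacement. Assuming 120 per arm and equal risks of 0.5% to 3%, at least one arm is empty with probability 80% falling to 5%. At such rates the chi-square has little power (7% to 22% for excesses of 1 to 2 points in the scenarios shown), so non-significance says little about the aim in Protocol 2.1. If the risks are nearer 5% vs 0%, power is 86% and this part of the concern falls away.

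A reader might infer that the trial intends to treat p>0.05 as proof of safety. Neither document says so; there is no safety hypothesis, margin or success rule. Nor does the chi-square give too many false positives at these rates. This is a cheap improvement to the SAP.

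**What to change.** In SAP Safety Analyses b), d) and e):

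- Report counts by arm and the risk difference (dapagliflozin minus usual care) with a 95% CI suited to sparse data. Miettinen-Nurminen or Newcombe would do; name one.
- Keep any p-value as a supplement.
- For death, name Firth-penalised logistic regression or a profile-likelihood interval for use when events are sparse.
- Reconcile items b) and d) with Protocol 10.0, either by following it or by stating that the SAP departs from it.
- State that p>0.05 will not be read as evidence of safety.

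The cost is SAP wording and a few lines of code, with no new data. The intervals will make the safety statements look less reassuring: even with no events in either arm, an excess of about 3 points is not excluded.
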